10.3 Clinical laboratory evaluations

10.3.1 Hematology, Chemistry and Urinalysis Parameters

Mandatory and optional clinical laboratory parameters are listed in [Section 12.1](#). Continuous laboratory variables summary statistics of actual values and change from Baseline will be presented by Exploratory Cohort, individual Confirmatory Cohorts and for overall combined Confirmatory Cohorts for the SS at each study visit and time point to the end of the Evaluation Period.

The number and percentage of subjects with possibly clinically significant treatment-emergent (PCST) value, PCST low values, and PCST high values will be summarized by individual Confirmatory Cohorts and for overall combined Confirmatory Cohorts for the SS. The summary of subject numbers will be reported as well. PCST criteria are included in the Appendices in the [Section 12.1](#).

The following listings will be provided:

- a separate subject data listing for PCST (all laboratory assessments for subjects with PCST values are to be included in the listing),
- all laboratory results of clinical chemistry, hematology and urinalysis laboratory tests.

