6.2 Exclusion criteria

Subjects are not permitted to be enrolled in the study if any of the following criteria are met:

- 1a. Subject receiving AED treatment other than PB, MDZ, PHT, LEV (≤ 60 mg/kg/day), or LDC for the treatment of seizures prior to or at the time of enrollment (Confirmatory Cohorts only).
2. Subject with seizures responding to any of the following: previous AED treatment immediately prior to BRV treatment, pyridoxine treatment, or correction of metabolic disturbances (hypoglycemia, hypomagnesemia, or hypocalcemia).
3. Subject requires extra corporeal membrane oxygenation.
4. Subject has seizures related to prenatal maternal drug use or drug withdrawal.
5. Subject has known severe disturbance of hemostasis, as assessed by the Investigator.
6. Subject has a poor prognosis for survival, as judged by the Investigator.
- 7a. Subject has 2x upper limit of normal (ULN) of any of the following: aspartate aminotransferase (AST), alanine aminotransferase (ALT), and alkaline phosphatase (ALP), with the following exception:

For subjects with perinatal asphyxia, elevation of AST, ALT or ALP < 5 x ULN is acceptable, if initial and peak elevation of liver function tests (LFTs) occurs within 5 days after birth, and the time course of LFT elevation is compatible with hepatic injury due to perinatal asphyxia.

The determination of ULN will be based on the subject's gestational age (GA) and the site's normal range values for the respective GA.8a. Subject has direct (conjugated) bilirubin levels $>2\text{mg/dL}$.

9. Subject requiring or expected to require phototherapy or exchange transfusion due to elevated bilirubin.
10. Subject with rapidly increasing bilirubin that may preclude the subject from inclusion in the study at the discretion of the Investigator.
11. Subject with a severe cardiac condition, including subject with a diagnosis or signs of long QT syndrome (LQTS), and subject with a family history of LQTS.

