3.6 Analysis sets

3.6.1 Safety Set

The Safety Set (SS) will consist of all enrolled subjects who take at least 1 dose of BRV. All safety analyses will be performed on the SS for the Exploratory Cohort and the Confirmatory Cohort(s).

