10.2 Adverse events

Treatment-emergent adverse events (TEAEs) are defined as AEs which have onset on or after the start date and time of initial study medication (BRV) administration.

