10.2.1 General summaries of AEs

A table with overall summary of AEs will be provided separately for Evaluation Period, Extension Period, Down-Titration Period, Safety Follow-up Period and for the entire study, the table will include:

- the numbers and percentages of subjects with at least one TEAE
- the number and percentage of subjects with serious TEAEs
- the number and percentage of subjects with non-serious TEAEs
- the number and percentage of subjects with a TEAE that led to permanent discontinuation of study medication
- the number and percentage of subjects with a drug-related TEAE
- the number and percentage of subjects with a drug-related serious TEAE
- the number and percentage of subjects with a severe TEAE
- the number and percentage of subjects with AE leading to death
- the number and percentage of subjects with TEAEs leading to death
- the number and percentage of subjects who died prior to the first BRV dose

The following summary tables of AEs/TEAEs will be provided by primary SOC and PT. Summaries will be presented by Exploratory Cohort and individual Confirmatory Cohorts and for overall combined Confirmatory Cohorts for the SS.

- Incidence of pre-treatment AEs

Pre-treatment AEs are defined as AEs that had onset strictly prior to the date/time of the first dose of BRV

- Incidence of TEAEs (for Evaluation Period, Extension Period, Down-Titration Period, Safety Follow-up Period and for the entire study)
- Incidence of serious TEAEs
- Incidence of non-serious TEAEs

- Incidence of TEAEs by maximum intensity
Each subject will be counted at most once per primary SOC or PT according to the maximum intensity of all AEs within that SOC or PT. Severe intensity will be assumed for AEs for which intensity is not specified.
- Incidence of drug-related TEAEs
Drug-related AEs are AEs for which the relationship to study medication is specified by the Investigator as Related or AEs for which relationship is not specified.
- Incidence of drug-related serious TEAEs
Drug-related AEs are AEs for which the relationship to study medication is specified by the Investigator as Related or AEs for which relationship is not specified.
- Incidence of TEAEs by relationship
- Incidence of non-serious TEAEs by relationship
- Incidence of serious TEAEs by relationship
- Incidence of fatal TEAEs by relationship
- Incidence of TEAEs leading to permanent discontinuation of study medication
- Incidence of TEAEs leading to death

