10.4.1 Vital signs

Observed values for SBP, DBP, respiration rate, heart rate, temperature and oxygen saturation will be summarized for each visit and time points. Changes from Baseline for SBP, DBP, heart rate, respiration rate, temperature, and oxygen saturation will be summarized for post-baseline visits and time points. Similar summaries will be provided for body weight.

Line graph plots of observed vital sign parameters mean values and change from baseline in vital sign parameters mean values will be presented by visit and time point.

The numbers and percentages of subjects with a PCST (possibly clinically significant treatment emergent) value, PCST low values, and PCST high value will be summarized for SBP, DBP, heart rate, and respiration rate by individual Exploratory Cohort, individual Confirmatory Cohorts and for overall combined Confirmatory Cohorts for SS. PCST criteria are based on FDA

Division of Neuropharmacologic Drug Products guidelines with some UCB-defined additions and are included in the Appendices in the [Section 12.1](#).

A listing of vital signs will be provided for the SS.

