12.2.3 Chemistry (without Bilirubin)

Parameter	low	high	Comment
Calcium mg/dL (mmol/L)	<7d: <6.5 (<1.63)	<7d: ≥12.4 (≥3.1)	Grade 2 toxicity based on DAIDS criteria ⁴
	≥7d: <7.8 (<1.95)	≥7d: ≥11.5 (≥2.88)	
Potassium mEq/L (mmol/L)	<3.0	>6.0	Grade 2 toxicity based on DAIDS criteria ⁴
Sodium mEq/L (mmol/L)	<130	≥150	Grade 2 toxicity based on DAIDS criteria ⁴
Glucose mg/dl (mmol/L)	<50 (<2.22)	>160 (>13.89)	Grade 2 toxicity based on DAIDS criteria ⁴
AST/ALT/ALP	n/a	>2.5 ULN	Grade 2 toxicity based on DAIDS criteria ⁴

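### The laboratory PCST count in SAP 10.3.1 is labelled treatment-emergent without any post-dose or Baseline condition, and its table leaves out the Exploratory Cohort.

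*SAP*

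**What the plan says.** **The count.** SAP 10.3.1 plans the number and percentage of subjects with a PCST value, a PCST low value and a PCST high value. These "will be summarized by individual Confirmatory Cohorts and for overall combined Confirmatory Cohorts for the SS. The summary of subject numbers" follows. The section sends the reader to 12.1 for the criteria, but 12.1 holds only the parameter lists; the limits are in 12.2. The liver-enzyme row in 12.2.3 reads "AST/ALT/ALP n/a >2.5 ULN". Neither 10.3.1 nor 12.2 gives a time window or a Baseline condition for a PCST value.

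**The same label for adverse events.** In SAP 10.2, treatment-emergent events are "defined as AEs which have onset on or after the start date and time of initial study medication (BRV) administration". SAP 10.2.1 tabulates the remainder separately: "Pre-treatment AEs are defined as AEs that had onset strictly prior to the date/time of the first dose of BRV".

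**Baseline.** SAP 3.4 defines a safety Baseline as the last value before the first BRV infusion. The PCST count does not use it.

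**Entry limits.** Protocol 6.2, criterion 7a, excludes at 2 x ULN and then makes an exception: "For subjects with perinatal asphyxia, elevation of AST, ALT or ALP" below 5 x ULN is acceptable if it starts and peaks within 5 days of birth and its time course fits asphyxia.

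**Cohorts.** SAP 3.6.1 calls for every safety analysis in both parts of the study. SAP 10 and protocol 13.4 call for laboratory summaries by cohort. The descriptive laboratory summary in 10.3.1 itself includes the Exploratory Cohort, and the vital-sign PCST table in 10.4.1 is given "by individual Exploratory Cohort, individual Confirmatory Cohorts and for overall combined Confirmatory Cohorts for SS".

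**The concern.** The label says that the abnormality arose on treatment; the rule behind it is only an absolute cut-off. For most parameters in most babies this may matter little. For liver enzymes, the eligibility criteria deliberately let in babies whose values already exceed the cut-off. In a single-arm study no concurrent control column would show the background rate, so a reader of this table has nothing in it to separate injury from asphyxia from a change after BRV.

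The cohort point is separate. Read as written, the sentence leaves the first neonates exposed to BRV out of a safety count that the plan's own general rules say should include them. Table 3.1 in SAP 3.10, which records departures from the protocol-defined analyses, does not mention this.

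**Working it through.** The plan states no figure on this point, so there is none to reproduce. The check compares the limits, then the cohorts, and then illustrates a possible size.

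**1. Liver-enzyme limits side by side (AST, ALT, ALP)**

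| Group | May enter with | PCST high | Overlap at entry |
|---|---|---|---|
| Perinatal asphyxia (exception in 7a) | below 5 x ULN | above 2.5 x ULN | 2.5 to 5 x ULN |
| All other babies | excluded at 2 x ULN | above 2.5 x ULN | none, since 2 < 2.5 |

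**2. What the rule does with such a baby.** Take an asphyxiated baby at 4 x ULN before BRV and 3 x ULN at a post-dose test. Since 3 > 2.5, the baby is PCST high although the value fell. Reading treatment-emergent as post-dose does not help, because the 3 x ULN value is post-dose. Persistence is plausible on the protocol's own terms: its withdrawal criteria (6.3) describe normalization of asphyxial elevations as taking until up to day 14 after birth, and Confirmatory safety tests fall at 24 and 96 hours (8.2.2).

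**3. The plan conditions on time or Baseline elsewhere.** Adverse events are split at the first dose (10.2, 10.2.1). Two of the four PDILI rows in SAP 12.3 require at least 2 x Baseline. The PCST limits have no counterpart.

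**4. Omitted cohort.** At least 6 Exploratory and 36 Confirmatory subjects are planned (SAP 2.4): 6 / 42 = 14.3% of planned subjects.

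**5. Illustration of size (assumptions, not data).** Let s be the share of the 36 Confirmatory babies who fall under the asphyxia exception, and q the share of those above 2.5 x ULN at entry. The expected number is 36 x s x q, and the chance of at least one is 1 - (1 - s x q)^36. Protocol 2.1 cites 42% of neonatal seizures following HIE. That is used as the middle value of s, as a proxy only. The other values of s, and all values of q, are assumed.

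| s | q = 0.10 | q = 0.30 | q = 0.50 |
|---|---|---|---|
| 0.20 | 0.7 babies (2.0%), P = 0.52 | 2.2 (6.0%), P = 0.89 | 3.6 (10.0%), P = 0.98 |
| 0.42 | 1.5 (4.2%), P = 0.79 | 4.5 (12.6%), P = 0.99 | 7.6 (21.0%), P > 0.99 |
| 0.60 | 2.2 (6.0%), P = 0.89 | 6.5 (18.0%), P > 0.99 | 10.8 (30.0%), P > 0.99 |

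For the middle cell: 36 x 0.42 x 0.30 = 4.5. These are babies already above the limit at entry. Under a post-dose reading, only those still above it after dosing would be counted, so the numbers could be smaller.

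**The case against.** The strongest reply is that little rests on this table. Four parts of it stand.

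- A reader might infer that asphyxial injury will be reported as a BRV liver signal or as an event of special interest. The documents do not support that. Protocol 11.1.1.3 has its own rule and raises the reporting limit to 5 x ULN for asphyxiated babies whose time course fits. SAP 10.3.2 gives PDILI its own criteria and its own summary by cohort.
- The pre-existing elevation stays visible. SAP 10.3.1 also plans actual values, change from Baseline, and a listing of all laboratory assessments for babies with a PCST value.
- A reader might infer that the omission hid data from the dose decision, or that Exploratory results go unreported. Neither follows. The DMC recommended the Confirmatory dose on 05 Nov 2020; protocol 13.8.1 provides it with its own safety summaries and listings, and SAP 4.3 assigns its analyses to a separate DMC SAP. The listings in 10.3.1 carry no cohort restriction.
- Over-flagging is the cautious direction for a screen. Simply dropping babies who were already abnormal at Baseline would lose one who rose from, say, 2.6 to 10 x ULN. The fix has to avoid that.

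A further argument is that the sponsor's statistical and program conventions, listed in SAP 11, may define a treatment-emergent laboratory value. They are not available here, so this cannot be excluded. The SAP neither states such a rule nor refers to one at this point.

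What the reply does not answer is that the count, run as written, puts the wrong label on some babies and leaves out a cohort.

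**Conclusion.** The point holds as a defect of one safety table. The laboratory PCST count carries a treatment-emergent label that its definition does not earn. The eligibility criteria make the mismatch concrete for AST, ALT and ALP between 2.5 and 5 x ULN in babies with perinatal asphyxia. The table's cohort list also contradicts the plan's general rules and its parallel vital-sign table, leaving out at least 6 of 42 planned subjects (14.3%).

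The number of mislabelled babies is not in the documents. The range of 0.7 to 10.8 of 36 shows only that the effect could be anything from negligible to large. It rests on HIE as a proxy for the asphyxia exception and on assumed entry shares, and should not be quoted as an estimate. No efficacy, PK or dose conclusion is affected. The correction is worth making because it is cheap and needs no new data.

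**What to change.** In SAP 10.3.1:

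1. Count a laboratory PCST value as treatment-emergent only if it is after the first BRV dose and either the Baseline value (SAP 3.4) did not meet the same criterion or the post-dose value is worse than a Baseline that already met it. State what counts as worse, for example further beyond the limit than at Baseline.
2. Show babies already PCST at Baseline separately, split by whether they worsened. A table of Baseline against worst post-dose PCST status would do this.
3. Add the Exploratory Cohort column, as in 10.4.1.
4. Point to 12.2 rather than 12.1 for the PCST criteria. SAP 10.4.1 has the same wrong pointer.

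The cost is SAP wording, one extra programming condition, one column and one more table. All the data are already collected.

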10.3.2 Potential Drug Induced Liver Injury

A summary of the number and percentage of subjects who met PDILI criteria at any point in time will be summarized overall, and by cohort for all subjects. Results from local laboratory testing should be included, if applicable. Subjects who meet one or more of the criteria for potential drug-induced liver injury (PDILI) at any point in time will be listed. The listing will display all assessments for which at least one of the criteria for PDILI (see [Appendix Error! Reference source not found.](#)) was fulfilled for a given subject, and will display all results obtained at that time for the specified variables associated with PDILI. Potential Hy's law cases will be flagged.

All PDILI events require immediate action, testing, and monitoring. The measurements and additional information required for the assessment of PDILI events when there is a reasonable possibility that they may have been caused by the IMP are included but not limited to those listed in laboratory measurements.

Additional PDILI information will also be listed. If specific PDILI information collected separately is matching to the entries in the standard eCRF pages collected for all subjects, the specific PDILI information will be added to the corresponding listing for the standard eCRF information. For information collected on top (eg, family history of PDILI, lifestyle) a new listing will be generated.

Suspected hepatic events will be listed for the SS.

10.4 Vital signs, physical findings, and other observations related to safety

Vital signs SBP (systolic blood pressure), DBP (diastolic blood pressure), respiration rate, temperature, oxygen saturation including apnea and heart rate are assessed throughout the study. Physical and neurological assessments include Sarnat scale for subjects with HIE, psychometric parameter N-PASS, and EEG.

10.4.1 Vital signs

Observed values for SBP, DBP, respiration rate, heart rate, temperature and oxygen saturation will be summarized for each visit and time points. Changes from Baseline for SBP, DBP, heart rate, respiration rate, temperature, and oxygen saturation will be summarized for post-baseline visits and time points. Similar summaries will be provided for body weight.

Line graph plots of observed vital sign parameters mean values and change from baseline in vital sign parameters mean values will be presented by visit and time point.

The numbers and percentages of subjects with a PCST (possibly clinically significant treatment emergent) value, PCST low values, and PCST high value will be summarized for SBP, DBP, heart rate, and respiration rate by individual Exploratory Cohort, individual Confirmatory Cohorts and for overall combined Confirmatory Cohorts for SS. PCST criteria are based on FDA

Division of Neuropharmacologic Drug Products guidelines with some UCB-defined additions and are included in the Appendices in the [Section 12.1](#).

A listing of vital signs will be provided for the SS.

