5.1.4 Planned number of subjects and sites

At least 42 evaluable subjects will be enrolled in this study, with at least 6 subjects in the Exploratory Cohort evaluable for the determination of BRV plasma concentrations and at least 36 subjects with evaluable PK data in the Confirmatory Cohorts (at least 12 subjects in each of the 3 Confirmatory Cohorts). At least 2 subjects undergoing hypothermia treatment will be included in the Exploratory Cohort and each of the 3 Confirmatory Cohorts.

The number of subjects in the Exploratory Cohorts might be increased, if deemed necessary, following the analysis of PK data.

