^o Laboratory assessment (safety) only required for Unscheduled Visits performed during the BRV Extension Period.

Table 5–4: Schedule for PK Sampling (Exploratory Cohort)

Assessment	48-hour Evaluation Period					
	Time relative to the start of the most recent BRV infusion					
	Day 1			Day 2 ^a		
BRV PK samples ^c	X	X	X	X	X	X
AED PK sample		X ^d				

AED=antiepileptic drug; BRV=brivaracetam; h=hours; min=minutes; PK=pharmacokinetic(s)

Note: Blood for PK samples should be drawn from a line different to that of the BRV infusion.

^a Blood sampling is only needed on Day 2 if subjects are dosed with BRV on Day 2.

^b The first PK sample should be collected 30 to 60 minutes after the start of the BRV infusion.

^c The BRV PK sampling timepoints for the first 3 samples of the Exploratory Cohorts are as follows: 30 to 60 minutes, 2 to 4 hours, and 8 to 12 hours after the start of the most recent BRV infusion. The second set of 3 samples will be collected at the same timepoints on the second day of the 48-hour Evaluation Period.

^d The AED PK sample should be collected 3 hours after the start of the initial BRV administration.

This document cannot be used to support any marketing authorization application and any variations thereof.
PUBLIC COPY

Table 5–5: Schedule for PK Sampling (Confirmatory Cohorts)

Assessment	96-hour Evaluation Period											
	Time relative to the start of the most recent BRV infusion											
	Day 1			Day 2			Day 3			Day 4		
	30-60mi n ^a	2-4 h	8-12 h	30-60m in	2-4 h	8-12 h	30-60m in	2-4 h	8-12 h	30-60m in	2-4 h	8-12 h
BRV PK samples ^b	X	X	X	(X)	(X)	(X)	(X)	(X)	(X)	(X)	(X)	(X)
AED PK sample		X ^c										

AED=antiepileptic drug; BRV=brivaracetam; h=hours; PK=pharmacokinetic(s); min=minutes; (X)=optional for that day

Note: Blood for PK samples should be drawn from a line different to that of the BRV infusion.

^a The first PK sample will be collected 30 to 60 minutes after the start of the BRV infusion.

[figure not shown]
^b The BRV PK sampling timepoints for the first 3 samples of the Confirmatory Cohorts are as follows: 30 to 60 minutes, 2 to 4 hours, and 8 to 12 hours after the start of the most recent BRV infusion. The second set of 3 PK samples will be collected within the same timeframes as the first set on one of the following days: either Day 2 (post-24 hours), OR Day 3 (post-48 hours) OR Day 4 (post-72 hours). It is acceptable if these samples are drawn on different days.

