2.3 Study design and conduct

N01349 is a Phase 2/3, multicenter, open-label, single-arm study to evaluate the PK, efficacy, and safety of BRV in neonates with repeated EEG seizures.

N01349 consists of a 2-step design and includes a descriptive comparison with a historical control group (matched in age and condition) from literature treated with AEDs per System Organ Class (SOC) and diagnostic methods.

For the Exploratory Cohort (first step), enrolled subjects will receive one or more AEDs for the treatment of ENS per SOC (first-line, second-line, or subsequent treatment; choice of treatment, dose and dosing frequency are at the discretion of the Investigator) prior to receiving BRV.

Subsequently, an initial iv dose of BRV (0.5mg/kg) will be administered. At the discretion of the Investigator, 3 additional iv BRV doses, up to a total of 4 iv BRV doses (0.5 mg/kg bid), can be administered during the 48-hour Evaluation Period. This treatment, which is the first use of BRV in neonates, is 4-fold less than the highest dose of 4mg/kg/day (2mg/kg bid) that has been used previously in infants \geq 1 month old.

For the Confirmatory Cohorts (second step), 3 consecutive cohorts are planned, and the efficacy of BRV will be evaluated. The iv dose of BRV selected for the Confirmatory Cohorts will be determined by the evaluation of BRV plasma concentrations from the Exploratory Cohort, as well as by previous PK modeling of N01263 data, to be within the range of plasma concentrations observed in children \geq 1 month old who received 4mg/kg/day. A dosage of BRV 4mg/kg/day for neonates is predicted to be approximately equivalent to the highest BRV dosage (200mg/day) that has been studied in the adult Phase 3 program (eg, N01358 and N01258). The PK and safety of BRV will be evaluated in all cohorts.

The recommendation to confirm or adjust the originally calculated BRV dose of the Confirmatory Cohorts of study N01349 will be given by the Data Monitoring Committee (DMC) after review of PK and safety data of the Exploratory Cohort.

At the end of the Evaluation Period, subjects from both the Exploratory and Confirmatory Cohorts may enter the BRV Extension Period.

All subjects who participate in the BRV Extension Period must be offered entry into a long-term study, if they meet the eligibility criteria. Before entering the long-term study, subjects must be on oral BRV.

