4.8 Examination of subgroups

All efficacy variables will be analyzed by

1. Primary cause of seizure subgroups: HIE, ischemic stroke, intracranial hemorrhage, epileptic encephalopathy/genetic epilepsy, intracranial infection, brain malformation, inborn error of metabolism, undetermined causes, other.
2. Concomitant use of hypothermia subgroups: yes, no.

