9.1.2 Confirmatory Cohorts

Based on the plasma samples collected for the Confirmatory Cohorts, PK parameters AUC, C_{max} , $t_{1/2}$, volume of distribution, and clearance, will be summarized.

Summary tables will be provided for the PK parameters, for plasma concentrations of BRV, ucb-42145, ucb-100406-1, ucb-107092-1 and of concomitant AEDs (PB and PHT) for each Confirmatory Cohort separately and overall for combined Confirmatory Cohorts.

Summary tables for subjects with concomitant hypothermia use will be provided for each Confirmatory Cohort separately and overall for combined Confirmatory Cohorts.

Individual plots of plasma concentrations over time will be provided for each Confirmatory Cohort separately and overall for combined Confirmatory Cohorts.

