10 SAFETY ANALYSES

All safety analyses will be presented for the SS. Descriptive summaries will be presented overall and by cohorts for

- AEs,

- SAEs,
- physical and neurological examination assessments,
- laboratory results,
- vital signs, (SBP, DBP, respiration rate, heart rate, temperature and oxygen saturation)
- body weight, and
- head circumference.

Following subject characteristics related to safety will also be summarized descriptively:

- cooling status variables (target low body temperature, age since birth when cooling began, duration of cooling [date and start and stop time of cooling], and timing of cooling in relation to first dose of BRV),
- rewarming status variables (duration of rewarming [date and start and stop time of rewarming] and timing of rewarming in relation to first dose of BRV),
- the mother's use of AEDs (including BZD and opiates) at childbirth,
- N-PASS score,
- Thompson score,
- the primary cause of seizure (HIE, hemorrhage, or infarction; CNS malformations; CNS infections; undetermined causes), and
- EEG parameters for the assessment of sedation.

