10.4.2 Hypothermia treatment

Listing of hypothermia treatment will be provided for the SS. It will include information if subject received hypothermia treatment, age since birth, age since birth when cooling began, target low body temperature, date and time cooling began, date and time cooling ended, duration of cooling (in days, hours and minutes, date and time cooling ended minus date and time cooling started plus 1 minute), timing of cooling in relation to first BRV dose (in hours, relative day and time), date and time rewarming began, date and time rewarming ended, duration of rewarming (in days, hours and minutes, date and time of end of rewarming minus date and time of start of rewarming plus 1 minute) and timing of rewarming in relation to first dose of BRV (in hours, date and time of start of rewarming minus date and time of first BRV dose).

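### The vital-sign change tables in SAP 10.4.1 are not split by hypothermia status, so the mean temperature change in every cohort partly reflects cooling or rewarming

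*SAP*

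**What the plan says.** SAP 10.4.1 plans observed values and changes for six vital signs: "Changes from Baseline for SBP, DBP, heart rate, respiration rate, temperature, and oxygen saturation will be summarized for post-baseline visits and time points". It adds line plots of the means and of the mean changes, and counts of possibly clinically significant (PCST) values for blood pressure, heart rate and respiration rate. It names no split by cooling. SAP section 10 sets the grouping for all safety output: "Descriptive summaries will be presented overall and by cohorts for" the listed items, vital signs among them.

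Cooled babies are required everywhere: "At least 2 subjects undergoing hypothermia treatment will be included in the Exploratory Cohort and each of the 3 Confirmatory Cohorts" (Protocol 5.1.4). SAP 3.4 takes the last reading before the first BRV infusion as the safety Baseline, with no condition on thermal state. The design is uncontrolled: "N01349 is a Phase 2/3, multicenter, open-label, single-arm study".

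The SAP does use hypothermia status elsewhere. Section 4.8 has "Concomitant use of hypothermia subgroups: yes, no", but under a lead-in limited to efficacy variables. For PK, section 9.1.2 says "Summary tables for subjects with concomitant hypothermia use will be provided for each Confirmatory Cohort separately and overall". For safety, section 10.4.2 lists start and end of cooling and rewarming, including "timing of rewarming in relation to first dose of BRV", and section 10 also summarizes these as subject characteristics. No planned table or plot crosses them with vital signs.

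**The concern.** Temperature is the quantity that cooling and rewarming deliberately change. A baby dosed while cooled has a cooled Baseline, and any reading after rewarming is then a rise from Baseline with no drug involved. A baby whose cooling begins after the Baseline reading shows a fall. Because every cohort mixes cooled and non-cooled babies, the by-cohort tables cannot separate the two, and there is no control group in which the same shift would appear.

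Change from Baseline in vital signs, and separately in heart rate, are stated safety variables (Protocol 4.3.2, SAP 2.2.3.2). If the tables are produced as written, the mean temperature change at each time point mixes two causes, and a rewarming rise can cancel a genuine fall. The mean plots and the heart-rate PCST counts are pooled in the same way.

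**Working it through.** The plan gives no figure to reproduce here, and no formal sample-size calculation was done. The planned counts are consistent: 6 + 3 × 12 = 42.

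**Inputs from the documents**
- Minimum cooled, Exploratory Cohort: 2/6 = 33.3%.
- Minimum cooled, each Confirmatory Cohort: 2/12 = 16.7%; combined: 6/36 = 16.7%.
- Post-Baseline readings run to 96 hours in the Confirmatory Cohorts and to 48 hours in the Exploratory Cohort.

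**Assumptions not in the documents**
- Temperature rise on rewarming: 1 to 4 C.
- Heart-rate rise on rewarming: 10 to 30 bpm.
- Share of cooled babies who rewarm between Baseline and the time point: one half to all.
- No drug effect, and no change in babies who are not cooled.

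**Formula:** shift in pooled mean change = (share cooled) × (share of those rewarmed by the time point) × (rise on rewarming).

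**Temperature**

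| Group | All rewarmed | Half rewarmed |
|---|---|---|
| Combined Confirmatory, 6/36 | 6/36 × 1 = +0.17 C to 6/36 × 4 = +0.67 C | +0.08 to +0.33 C |
| Exploratory, 2/6 | 2/6 × 1 = +0.33 C to 2/6 × 4 = +1.33 C | +0.17 to +0.67 C |

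Cooling begun after Baseline gives the same sizes with a minus sign, for an equal drop in temperature.

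**Heart rate, all rewarmed.** Confirmatory: 6/36 × 10 = +1.7 bpm to 6/36 × 30 = +5.0 bpm. Exploratory: 2/6 × 10 = +3.3 bpm to 2/6 × 30 = +10.0 bpm. Even the direction of this effect is assumed.

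**Masking.** Suppose every baby has a true fall of 0.5 C and the six cooled babies also rise by 3 C on rewarming. Non-cooled babies change by −0.5 C and cooled babies by 3 − 0.5 = +2.5 C. The pooled mean is 30/36 × (−0.5) + 6/36 × 2.5 = −0.42 + 0.42 = 0, so the table shows no change.

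**After a split.** Among babies not cooled at or after Baseline, the share cooled in the formula is zero and so is the shift.

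**The case against.** The case for leaving the plan alone has several fair parts.

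- *Rank and purpose.* Adverse events are the secondary safety variable; vital signs are among the other safety variables. SAP 4.5 makes all analyses descriptive, with no tests, and nothing in the plan attributes a vital-sign change to BRV. This stands and limits the weight of the point. It does not remove it, because an uncontrolled change from Baseline after dosing will be read with the drug in mind.
- *The information is available.* Vital signs and cooling times are both listed per subject, and about 42 babies can be cross-read. True, but the planned means and plots would still be mixed, and matching listings by hand is not a prespecified display.
- *No departure from the protocol.* Protocol 13.4 asks for no hypothermia split of safety data, so the SAP does not contradict it. Temperature has no PCST limit, so no false temperature flag can arise. Both stand.
- *Small cells.* With a minimum of 2 cooled babies per cohort, splitting each Confirmatory Cohort would give very sparse tables. This stands, and is why the split is proposed only for the combined Confirmatory Cohorts and the Exploratory Cohort.

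Two stronger readings are tempting but unsupported. A reader might take the 42% in Protocol 2.1 as the cooled share and arrive at shifts such as 0.42 × 4 = 1.7 C or 0.42 × 40 = 17 bpm. That 42% is the share of neonatal seizures following HIE in a cited population study, not a share of cooled babies in this trial, and the calculation also assumes that all of them rewarm in the window.

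A reader might also infer that the PK comparison by hypothermia is halved, because the second set of three samples may come from "either Day 2 (post-24 hours), OR Day 3 (post-48 hours) OR Day 4 (post-72 hours" and so follow rewarming. No passage says that the six samples are averaged with equal weight, the primary PK variable is the concentration after the first dose on Day 1, and the population PK model has its own plan (Protocol 13.3.2), which is not among these documents.

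**Conclusion.** The gap is real. Followed as written, SAP 10.4.1 gives a mean temperature change that partly measures cooling and rewarming, in either direction, in every cohort. At the protocol minimum and under an assumed 1 to 4 C rise, the combined Confirmatory mean moves by +0.17 to +0.67 C if all cooled babies rewarm between Baseline and the time point, and by half that if half do. The 6/36 is a floor on the number cooled; a larger share scales the shift in proportion. The documents give neither the rise nor the number rewarmed by each time point. For heart rate a similar effect is possible, but the documents neither state nor quantify it.

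The point does not show that the plan claims a drug effect where there is none, or that the PK results are distorted by a known amount. It is an inexpensive improvement to a descriptive safety analysis that should be made before the tables are produced.

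**What to change.** In SAP 10.4.1:

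1. Keep the pooled tables and plots.
2. Add the same tables and mean plots by hypothermia status, for the Exploratory Cohort and the combined Confirmatory Cohorts: babies not cooled at or after Baseline, and babies cooled at any time from Baseline. State that a baby still being rewarmed at Baseline belongs to the second group.
3. In the vital-signs listing, flag each reading taken during cooling or after the recorded start of rewarming, using the times in 10.4.2.
4. Show the heart-rate PCST counts by the same status.
5. State that BRV-related change in temperature and heart rate is read primarily from the babies not cooled, with the cooled babies reported alongside.

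For PK, a flag in the listing showing whether each sample was drawn during cooling or after the start of rewarming is enough.

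No new data are needed, since the start and stop times are already collected. The cost is a little extra programming to set the status and the flags, and small cells for cooled babies: possibly as few as 2 in the Exploratory Cohort and 6 in the combined Confirmatory Cohorts.
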